5 BIOSPECIMEN COLLECTION

5.1 BIOMARKER STUDIES FOR RESEARCH

1) Blood/Urine

Sampling Time Points for biomarker studies/ biospecimen banking

	Baseline	C 2 D1 (within 3 days prior)	C 4 D1 (within 3 days prior)	C 7 D1 (within 3 days prior)	Every 3 cycles starting at cycle 7 D1 (within 3 days prior)	Every 6 cycles starting at cycle 7 D1 (within 3 days prior)	Disease progression	At CR
Blood for biomarker analysis	x	x	x	x		x	x	x
Bone marrow*	x						x	x
Blood/Urine Biopspecimen storage bank	x	x	x	x	x		x	x

- Blood samples for biomarker studies will be collected from all patients at baseline, after cycles 1, 3, and 6, and then after every 6 cycles while receiving lenalidomide therapy, until completion of the study. The samples will be batched for later analysis.
- The assays will be run on the batched samples for first ten patients at baseline, and after cycles 1, 3, and 6 to determine the appropriate time points of assays for the subsequent patients.
- Blood and urine specimens will be collected from all patients who agree to participate in optional studies and stored for establishing biospecimen storage bank. These specimens will be collected at baseline, after cycles 1, 3, and 6 and after every three cycles while receiving lenalidomide. Specimens will also be collected and stored at the time of documented CR and disease progression. IRB approval will be obtained before using any samples to conduct studies that are not described within this protocol.

Abbreviated Title: Revlimid maintenance for MM

Version Date: 01/06/2017

- d. Collection and storage of peripheral blood and urine for biospecimen storage bank is outlined in appendix C.
- e. Processing of peripheral blood for biomarker studies is outlined in appendix D.
- f. At any given time, up to 100cc of peripheral blood will be collected. The amount of blood collected will be dictated by the number of experiments to be performed, and by the patient's peripheral blood count.
- g. The standard number of peripheral blood tubes drawn for storage at each of the above time points may include but are not limited to the following: one 7-8 mL serum tube, one 7-8 mL plasma heparinized tube, and one 7-8 mL EDTA tube.
- h. The standard number of peripheral blood tubes drawn for biomarker analysis at each of the above time points may include but are not limited to the following: two 7-8 mL plasma heparinized tubes.
- i. At any given time, approximately 45 mL of urine will be collected into a standard urine collection cup and sent for analysis and storage at each of the above timepoints.
- j. Sample Requirements and Handling: The date and exact time of each blood draw should be recorded on the sample tube. Serum samples should be kept at room temperature for 30-60min prior to being refrigerated. Please page [name] lab at [name] for immediate pick-up.

2) Bone Marrow

Effective with Amendment D, bone marrow aspirate and biopsy will be obtained for research studies at the discretion of the PI.

- a. Bone marrow specimens (aspirate and biopsy) will be collected for at baseline, and then at the time of documented CR or disease progression. Bone marrow samples will be used to determine the molecular characteristics of the tumor cells and the expression of CCRN by gene expression profiling and quantitative PCR.
- b. Additional bone marrow samples for other biomarker studies will be obtained at the discretion of PI, if patients are willing.
- c. Collection of bone marrow, sorting of bone marrow and storage of bone marrow samples is outlined in appendix F.
- d. Biomarker studies associated with bone marrow specimen will be performed and related to clinical outcome if the results of the study indicate a clinical or translational rationale for analyzing the samples. Such studies may include but are not limited to the following:
 - i. Pathology/Immunohistochemistry: Bone marrow biopsy and aspirate will be sent to Clinical Center Department of Laboratory Medicine, Hematology Service for morphological evaluation by [name] and

[name], PhD. Immunohistochemical staining will be performed under the direction of [name]. Plasma cell burden will be assessed using immunohistochemistry markers such as CD 138, light chains, CD56 etc.

- ii. Flow cytometry: Immunophenotyping of aberrant plasma cells by flow cytometry currently involves, but is not limited to, the use of the following reagents: CD138, CD19, CD45, CD38, and CD56. Characteristic changes in immunophenotypically abnormal plasma cells (CD138 positive) include but are not limited to absent CD19 and CD45, decreased CD38, and increased CD56. These studies will be performed under the direction of [name] of the flow cytometry unit in the NCI Laboratory of Pathology.
- iii. Cell Sorting, molecular characterization - Marrow aspirate will be sent to the Lymphoid Malignancies Branch lab and sorted into CD 138 + and CD 138 – fractions. For questions regarding these samples, please contact [name] at [contact].
 - GEP profiling: CD138+ plasma cells will be purified from bone marrow aspirates harvested at each indicated time point. GEP will be performed in the Lymphoid Malignancies Branch lab using the Affymetrix U133 Plus 2.0 microarray platform. Gene expression profiles will be analyzed to identify potential markers of response to lenalidomide such as CCRN and markers for progression. Changes in selected genes will be confirmed by quantitative PCR if suggested to be related to response or progression.
 - Both CD 138+ and CD 138- fractions will be collected, batched, and entered into a biobank. See section **5.3.1** and Appendix F in section **18** for storage of bone marrow biobank.

5.2 BIOMARKER STUDIES: METHODS

While it has been shown that lenalidomide-induced NK cell activation is IL-2 dependent, the specific subset of cells responsible for mediating this effect has not been clearly elucidated. To conduct a comprehensive evaluation of a range of immune cells in relation to lenalidomide maintenance therapy, we will include analyses of B-, T-, NK and NKT cells and important signaling cytokines.

- **Phenotypic analysis of PBMCs:** Patients' PBMCs will be FACS-sorted into NK cells (CD3⁻CD16⁺CD56⁺), CD4 (CD3⁺CD4⁺), and CD8 (CD3⁺CD8⁺) T-cell subsets. The percentage of T cells (CD4, CD8), NKT and NK cells will be determined by phenotypic analysis of peripheral blood mononuclear cells (PBMCs) stained for CD56, CD3, CD4, CD8, and CD16. To obtain total numbers per milliliter of peripheral blood, the percentage of CD4 T or NK cells will be multiplied by the total lymphocyte count.
- **Phenotypic analysis of B cell subsets:** B cell subsets will be analyzed by phenotypic analysis of PBMCs stained for CD19, CD38 CD45, CD27 and CD138.

- **Proliferation assay for human T cells (CD4 and CD8):** 100 μ l of PBMC (1 x 10^6 cells/ml) will be added to each well of a in a 96-well round-bottom plate. The plate is coated with 100 μ l anti-CD3 (OKT3; eBioscience) at a concentration of 10 μ g/ml. Incubate plate in a humidified 37°C, 5% CO₂ incubator. All cells are cultured in medium RPMI 1640 (Mediatech, Inc., Herndon, VA) supplemented with 10% heat inactivated human AB serum (Gemini Bio-Products, Woodland, CA); 100 units/ml penicillin and 100 μ g/ml streptomycin (Mediatech, Inc.); 2 mM L-glutamine (Mediatech, Inc.). Cells are incubated for 3 days. Proliferation will be assessed by [³H]thymidine (1 μ Ci [0.037 MBq] per well) (Perkin-Elmer, Boston, MA) incorporation pulsed on day 4 and quantified 18 hours later using a liquid scintillation counter (Wallac, Gaithersburg, MD). All experiments will be performed in triplicate.
- **Functional NK analysis:** A 4-h ¹¹¹In-release assay will be used to measure NK activity in patients. Cell line K562 will be used as target. Target cells will be labeled with 50 μ Ci of ¹¹¹In-oxyquinoline in a volume of 0.25 ml of RPMI-1640 for 15 min at 37°C according to a modification of the procedure described by Wiltrot et al [48]. Target cells (1 x 10⁴) in 50 μ l will be added to each well of assay plates containing 96-U-bottom wells. Effector cells (sorted NK cells) to target cell (E/T) ratios of 50:1, 25:1, 12.5:1 and 6.25:1 will be assayed. The plates will be incubated for 4-h at 37°C in a humidified atmosphere containing 5% CO₂. Supernatants will be harvested for gamma counting using Skatron Harvesting Frames. Experiments will be carried out in triplicate. Specific lysis will be calculated using the formula:

$$\text{Lysis (\%)} = \frac{\text{Observed release (cpm)} - \text{Spontaneous release (cpm)}}{\text{Total release (cpm)} - \text{Spontaneous release (cpm)}} \times 100$$

- **Regulatory T cell (Treg) and MDSC phenotype:** The number and phenotype of Tregs in PBMCs from patients in this study will be determined by 9-color flow cytometry analysis. Cells will be resuspended in staining buffer (phosphate-buffered saline containing 3% fetal bovine serum) and stained for CD4, CD25, CD127, FoxP3, CTLA-4, CD45RA, PDL-1, DR and CD8. The ratios of Treg to effector cells will also be analyzed. MDSCs will be analyzed by staining for CD34, CD33, CD11b, CD15, CD13, CD14 and DR.
- **Chemokine and Cytokine Assay:** The presence of IL-4, IL-10, IL-8, IL-13, TNF-alpha, IFN-gamma, IL-12p70, GM-CSF, IL-5, and IL-6 in serum obtained from patients pre- and post-treatment will be determined using a multi-plex assay (Meso Scale Discovery, Gaithersburg, MD). Assays will also be performed for cytokines such as TGF-beta, IL-17, VEGF and IL-23.
- **Other Assays:** Using flow cytometry and immunohistochemistry, we will determine selected tumor cell antigen targets including, but not limited to MUC1, Brachyury, PD1 ligands, MAGE-A, and NYESO. Patient serum and bone marrow samples will be evaluated for previously studied prognostic markers including M-spike, percent bone marrow plasma cells, serum free light-chain ratio, total immunoglobulin levels,

immunophenotype by flow cytometry, albumin, and β 2-microglobulin. Patients' tumor cells will be characterized by gene expression profiling to enhance our understanding of lenalidomide efficacy and safety in a genetically diverse tumor population.

- **Future Assays:** The information obtained from this study regarding immune effector cells in MM will provide the framework for the development of immune-based therapeutic options like novel vaccines or monoclonal antibodies, and the development of therapies designed specifically to increase NK cell cytotoxicity against MM. It will also allow for analysis of myeloma cell-immune cell interactions.

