Lenalidomide can augment NK cell number, cytotoxicity and NK cell–driven antibody-dependent cell-mediated cytotoxicity (ADCC) in several ways [14]. In vitro studies have shown that peripheral blood mononuclear cells (PBMCs) are required for lenalidomide-induced NK cell function, and this is achieved indirectly through activation of nuclear factor of activated T cell 2 (NFAT2) in T cells [20, 21]. In this way, lenalidomide activates T cells to produce IL-2, which in turn stimulates NK cell activation and function against MM [20]. Lenalidomide causes enhancement of antigen-specific CD8+ T-cell cytotoxicity, upregulation of Fc-gamma receptor signaling leading to increased NK cell activity, and activation of NKT cells [14]. Lenalidomide has been shown to increase CD16 expression on NK cells and facilitate ADCC against MM [22]. Lenalidomide can also down-modulate suppressor of cytokine signaling (SOCS) 1 expression in NK cells, resulting in a higher sensitivity to activating stimuli in the microenvironment [23]. Finally, lenalidomide also appears to favorably modulate the balance of NK cell activating and inhibitory ligand expression on MM targets. This action of lenalidomide may be of particular interest as initiation of a cytotoxic response by an NK cell is mediated through balance of signals obtained through inhibitory receptors such as killer immunoglobulin-like receptors (KIRs) and CD94–NKG2A [24], and activating receptors including NKG2D, DNAM-1, and Nkp46 [24]. Lenalidomide up regulates expression of ULBP-1 on MM cells and decreases expression of PD-L1, which both result in improved NK cell surveillance, recognition and lysis of MM tumor targets [26, 27]. Changes in NK cell receptor ligand expression on MM cells and, hence, their resistance to NK cell–mediated killing may underlie the development of more proliferative and refractory plasma cell clones as MM progresses [28, 29] and treatment with lenalidomide in maintenance setting may provide a means to promote NK cell–mediated control over MM .

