3 STUDY IMPLEMENTATION

3.1 STUDY DESIGN

- Patients with newly diagnosed or relapsed MM with stable disease or better clinical response after induction or re-induction treatment will be enrolled on this phase II study and treated with a maintenance dose of lenalidomide 10 mg daily on days 1 to 21 of repeated 28-day cycles.
- Patients who complete at least 3 cycles will be evaluable for primary endpoints. Patients who do not complete three cycles of therapy will not be included in the analysis of primary or non-primary endpoints; and will be replaced by new patients.
- Using flow cytometry on peripheral blood, the four primary outcomes of T cell (CD4, CD8), NKT and NK cell numbers will be measured at pre-specified treatment time points to determine the difference in the counts of these parameters for each patient.

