8 STATISTICAL CONSIDERATIONS

8.1 STUDY DESIGN/PRIMARY ENDPOINTS

This is a single arm, single stage, phase II trial to evaluate maintenance therapy with the immunomodulatory agent lenalidomide in treated MM patients who have stable or responsive disease. After screening, eligibility determination, and enrollment; subjects will receive lenalidomide 10 mg by mouth daily on days 1-21 of a 28-day cycle. Subjects may continue lenalidomide until disease progression, diagnosis of new malignancy, unacceptable toxicity, investigator discretion, or voluntary withdrawal. When necessary, lenalidomide will be held and restarted in accordance with accepted clinical dose modification strategies.

The primary objective of this study is a longitudinal assessment of T cell (CD4, CD8), NKT and NK cell populations during the course of lenalidomide maintenance therapy in patients with MM. Using flow cytometry on peripheral blood obtained at baselines and after 3 cycles of therapy, we will determine the primary measures at both time points. Comparisons at other time points will be considered exploratory..

With 28 patients enrolled, we will have 80% power to detect an effect equal to 0.67 SD of the difference in counts (0.67 SD effect size) of T cells (CD4, CD8), NKT and NK cells with a two-tailed paired t-test and a significance level of 0.013 for each test. Thus, using a strict Bonferroni adjustment, we would have an overall significance level of 0.05 for the four tests. In practice, a less overly conservative Hochberg adjustment may be used instead of a Bonferroni adjustment. In addition, if the difference in the numbers of any type of cells is not normally distributed ($p < 0.05$ by a Shapiro- Wilks test), then a Wilcoxon signed rank test will be performed instead.

Results will be presented in a descriptive format.

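### The only NK phenotype in section 5.2 requires CD16, which the protocol says lenalidomide raises, so a CD16 shift could be counted as an increase in NK cells

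*Combined protocol and SAP*

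**What the plan says.** Section 5.2 (Phenotypic analysis of PBMCs) defines NK cells once. The sorting sentence reads "PBMCs will be FACS-sorted into NK cells (CD3⁻CD16⁺CD56", with a plus sign closing the bracket: CD3-negative and positive for both CD16 and CD56. The next sentence says that the percentages of T, NKT and NK cells come from cells "stained for CD56, CD3, CD4, CD8, and CD16", and gives no phenotype of its own. The absolute number is then formed as follows: "the percentage of CD4 T or NK cells will be multiplied by the total lymphocyte count". No rule covers CD56-positive cells that are negative or dim for CD16.

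Section 1.2, on the drug's effect on NK, NKT and T cells, states: "Lenalidomide has been shown to increase CD16 expression on NK cells and facilitate ADCC against MM".

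Section 3.1 names "the four primary outcomes of T cell (CD4, CD8), NKT and NK cell numbers". Section 8.1 bases the primary comparison on "peripheral blood obtained at baselines and after 3 cycles of therapy", in a single arm. It gives the design figure: "With 28 patients enrolled, we will have 80% power to detect an effect equal to 0.67 SD of the difference in counts", using a two-tailed paired t-test at 0.013 per test.

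**The concern.** A cell count used as an endpoint should not depend on a marker that the treatment is expected to change. Here the phenotype requires CD16, and the protocol's own rationale says the study drug raises CD16 on NK cells. A CD3-negative CD56-positive cell below the CD16 threshold at baseline is not counted. If its CD16 rises above the threshold by the end of cycle 3, it is counted as an additional NK cell although no cell has been added.

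With no control arm, a phenotype shift and a true expansion both appear as a positive paired difference. A larger sample would not separate them, nor would the Hochberg adjustment or the signed-rank fallback in section 8.1. No total NK count, CD16-negative subset or CD16 intensity is listed as a readout that could do so.

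The distinction matters in this trial. Section 1.1 makes NK number primary and NK function secondary, section 1.2 cites a study in which number rose while cytotoxicity fell, and section 1.2 ties CD16 to ADCC, which is function. A count that depends on CD16 mixes the two.

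**Working it through.** **1. The plan's own figure.** Inputs from section 8.1: n = 28, effect 0.67 SD of the within-patient difference, two-sided alpha 0.013. Exact paired-t power comes from the noncentral t with 27 degrees of freedom and noncentrality 0.67 × √28 = 3.55. The result is 0.804, which agrees with the stated 80%. The sample size is not in question.

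**2. The bias.** Let T be the true number of CD3-negative CD56-positive cells per mL and f the share of them that are CD16-positive. The gated count is T × f, so the on-treatment to baseline ratio is (T1/T0) × (f1/f0). If T does not change, the apparent relative rise is f1/f0 − 1.

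Write x = 1 − f0 for the baseline share outside the gate. Since f1 cannot exceed 1, the rise is at most 1/(1−x) − 1 = x/(1−x). The documents do not give x. For an assumed range:

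| x | x/(1−x) |
|---|---|
| 5% | 0.05/0.95 = 5.3% |
| 10% | 0.10/0.90 = 11.1% |
| 20% | 0.20/0.80 = 25.0% |
| 30% | 0.30/0.70 = 42.9% |

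These are ceilings, reached only if every cell outside the gate crosses into it.

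**3. Against the planned test.** The documents give no SD of the difference, so it is assumed here as a fraction s of the baseline mean gated count. The artefact in SD units is (f1/f0 − 1)/s. Put through the power function of step 1, this gives the chance of a significant NK change at 0.013 when the true NK number is constant (nominal chance 0.013):

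| CD16+ share, f0 to f1 | Apparent rise | s = 20% | s = 30% | s = 50% | s = 75% |
|---|---|---|---|---|---|
| 0.90 to 0.95 | 5.6% | 0.14 | 0.06 | 0.03 | 0.02 |
| 0.90 to 1.00 | 11.1% | 0.61 | 0.26 | 0.08 | 0.04 |
| 0.80 to 0.90 | 12.5% | 0.74 | 0.34 | 0.11 | 0.05 |
| 0.80 to 1.00 | 25.0% | 1.00 | 0.95 | 0.50 | 0.21 |
| 0.70 to 0.90 | 28.6% | 1.00 | 0.99 | 0.64 | 0.28 |
| 0.70 to 1.00 | 42.9% | 1.00 | 1.00 | 0.96 | 0.64 |

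The result runs from negligible to decisive, and nothing in the documents fixes where in the table the trial would lie.

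**4. For scale.** The NK rise cited in section 1.2, from 2.20 to 3.90 × 10^5/mL, is 3.90/2.20 − 1 = 77%. To be wholly a CD16 shift, it would need a baseline CD16-positive share of at most 2.20/3.90 = 56%. That figure is for cycle 6 with dexamethasone, so it is not a benchmark for the cycle 3 comparison here.

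**The case against.** The strongest reply is that the protocol never says outright that the count uses the CD16-positive phenotype. That phenotype is in the sorting sentence, and sorted NK cells have their own use as effectors in the lysis assay. The sorting sentence also omits NKT cells, a primary outcome, so it cannot be the full definition of the primary counts. This stands. A reader might infer that the count is stated to be CD16-gated; it is only the natural reading of the one bullet that also derives the count. If another definition is meant, it is unstated for a primary outcome, and the same passage needs the same edit.

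Second, section 1.2 speaks of expression, not of the share of positive cells. Higher CD16 on cells that are already positive leaves the count unchanged, and with no threshold given, dim cells may already be counted. The cycle 3 sample is drawn on day 1 of cycle 4 or up to 3 days before, when dosing has been off since day 21, and the documents do not say whether a CD16 change would persist. This also stands. It makes the bias possible rather than demonstrated.

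Third, a reader might infer that the error carries into the secondary objective relating CRBN to NK number. The documents do not support that. Section 5.1 schedules marrow for this marker (printed there as CCRN) at baseline and then at CR or progression, and a baseline relationship precedes study drug.

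Fourth, CD16 may help specificity. Section 5.1 notes increased CD56 on abnormal plasma cells, and the count panel has no CD138 or CD38 to exclude them. The effect is probably small in blood, since plasma cell leukemia is excluded, but it is a reason to keep the CD16-positive count alongside.

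Finally, section 8.1 presents results descriptively. That lowers the stakes but does not remove the ambiguity in a formally tested primary outcome.

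**Conclusion.** The point holds as a possible bias in one of four primary outcomes, with moderate confidence. It rests on two things in the text, the only printed NK phenotype and the stated drug effect on CD16, and on two that are not: that the sorting phenotype also governs the count, and that some CD3-negative CD56-positive cells cross the threshold on treatment. With true NK number constant, the false rise is at most x/(1−x), or 5% to 43% for an assumed x of 5% to 30%. Whether that would produce a significant result depends on an SD that the documents do not give. They do not support the stronger conclusion that an observed NK increase would be an artefact, only that the planned analysis could not tell the two apart. The sample size and the 80% power are unaffected.

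**What to change.** In section 5.2:

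- State the gate for the NK count separately from the sort.
- Define the primary NK count as CD3-negative CD56-positive lymphocytes regardless of CD16.
- Report the CD16-positive and CD16-negative/dim subsets, and CD16 intensity, as secondary readouts at each time point.
- Fix one CD16 threshold for all time points, including the first ten patients' samples, which section 5.1 assays first.
- Keep the CD3-negative CD16-positive CD56-positive count as a sensitivity analysis. If the two counts move together, a CD16 shift is not the explanation. If only the CD16-positive count rises, it is.

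A reader might infer that the physical sort for the lysis assay should change too. It need not: that would alter the effector population, which is more than a wording change.

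CD3, CD56 and CD16 are already stained and the samples are batched, so no new sample, reagent or visit is needed, and n = 28 stays. The one cost beyond wording is a possible small loss of specificity in the primary count, which the sensitivity analysis covers.

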2.2 SCREENING EVALUATION

2.2.1 Clinical evaluation must be completed within 4 weeks prior to study enrollment:

A complete history and physical examination with documentation of type of response (sCR, CR, VGPR, PR, MR or SD according to criteria described in section 6.2) to induction or re-induction treatment, the time interval from last treatment to documentation of response, and assessment of performance status using the ECOG scale must be performed prior to study entry. Patients will be evaluated for baseline neuropathy.

Abbreviated Title: Revlimid maintenance for MM

Version Date: 01/06/2017

2.2.2 The following studies and laboratory tests will be completed within 4 weeks prior to study entry:

- 2.2.2.1 CBC with differential
- 2.2.2.2 Reticulocyte count
- 2.2.2.3 Acute care panel, calculated creatinine clearance using Cockcroft-Gault formula (within 2 weeks prior to study entry)
- 2.2.2.4 Mineral panel, Hepatic panel, Uric acid, LDH, and Beta-2 Microglobulin
- 2.2.2.5 PT, PTT
- 2.2.2.6 Serum protein electrophoresis (SPEP) and immunofixation to assess for presence and quantity of monoclonal protein (M-protein)
- 2.2.2.7 Random urine sample for protein electrophoresis (UPEP) and immunofixation to assess for monoclonal protein in the urine (Bence-Jones proteinuria). Collect a 24 hour urine sample if necessary for confirmation of multiple myeloma response to prior (re)induction treatment, or if calculated creatinine clearance is <40 ml/min.
- 2.2.2.8 Serum free light chain studies
- 2.2.2.9 Quantitative immunoglobulins
- 2.2.2.10 Viral serologies:
 - Hepatitis B surface antigen
 - Anti Hepatitis C (HCV) antibody. If positive, will follow with HCV RNA PCR
 - HIV ELISA screening test. If positive, will follow with confirmatory Western Blot test
- 2.2.2.11 Review of bone marrow core biopsy or aspirate
- 2.2.2.12 Serum or urine pregnancy test in women of child-bearing potential (complete within 10-14 days and again within 24 hours prior to prescribing lenalidomide for cycle 1)
- 2.2.2.13 12-lead EKG
- 2.2.2.14 Skeletal survey of the axial and appendicular skeleton. Exception may be made if skeletal survey has been performed within the past 3 months and was found to be positive. In this case, films will be forwarded to the Clinical Center for confirmatory interpretation by the Department of Radiology.

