2.4 BASELINE EVALUATION

- 2.4.1 Research and clinical laboratory tests to be performed within 4 weeks of study entry and prior to starting therapy. Refer to section 5 for details on biospecimen collection and biomarker studies.
- 2.4.2 Peripheral Blood/Urine (see section 5)
 - 2.4.2.1 For storage and establishing a biobank (AppendixC in section [15](#))
 - 2.4.2.2 Flow cytometry and other assays (see section 5):
 - Phenotypic analysis of NK, NKT, and T cells
 - Phenotypic analysis of B cell subsets
 - Proliferation assays for human T cells (CD4 and CD8)
 - Functional NK cell analysis
 - Regulatory T cell and myeloid derived suppressor cell (MDSC) phenotype
 - Chemokine and cytokine assay
 - Selected tumor cell antigen targets
- 2.4.3 Bone Marrow (see section [5](#)). Bone marrow aspirate and biopsy will be used for histopathological evaluation, to determine the immunophenotyping of aberrant clonal plasma cells by multiparametric flowcytometry, CD 138+ and CD 138- fractions cell sorting with subsequent correlatives on both fractions, and the expression of CCRN by gene expression profiling and quantitative PCR.

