- e. FCBP with regular or no menstruation must have a pregnancy test (serum or urine) weekly for the first 28 days and then every 28 days while on therapy (including breaks in therapy); at discontinuation of lenalidomide and at Day 28 post the last dose of lenalidomide. Females with irregular menstruation must have a pregnancy test (serum or urine) weekly for the first 28 days and then every 14 days while on therapy (including breaks in therapy), at discontinuation of lenalidomide and at Day 14 and Day 28 post the last dose of lenalidomide (see Appendix A: Risks of Fetal Exposure, Pregnancy Testing Guidelines and Acceptable Birth Control Methods).
- f. Myeloma tests include serum protein electrophoresis, serum immunofixation, , serum free light chains, quantitative immunoglobulins, and beta-2 microglobulin will be performed at baseline, on Day 1 (within 3 days prior) of Cycle 2, Cycle 4, and Cycle 7, and thereafter every 3 cycles, at the time of documented CR, and at disease progression.
- g. Random urine sample for protein electrophoresis (UPEP) and immunofixation to assess for monoclonal protein in the urine (Bence-Jones proteinuria) will be performed at baseline, on Day 1 (within 3 days prior) of Cycle 2, Cycle 4, and Cycle 7, and thereafter every 3 cycles, at the time of documented CR, and at disease progression.
- h. Bone marrow aspirate and biopsy can be performed +/- 21 days of intended cycle day. Bone marrow aspirate and biopsy will be sent to Hematology Service of the Department of Laboratory Medicine and Flow cytometry for immunophenotyping of plasma cells. CD 138 sorting/GEP/quantitative PCR/ storage will be done in Molecular pathology or Lymphoid Malignancies Branch lab... For questions regarding these samples, please contact [name] at [contact]. Effective with Amendment D, bone marrow aspirate and biopsy will be obtained for research studies at the discretion of the PI.
- i. Blood for biomarker analysis will be collected on D1 (within 3 days prior) of Cycle 1, Cycle 2, Cycle 4, Cycle 7 and every 6 cycles thereafter.
- j. Skeletal survey to assess disease status will be performed at baseline. The skeletal survey at the time of documented CR or disease progression is optional.
- k. Variations of +/- 3 days of scheduled visits are permitted.

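### Are the four primary cell counts too loosely defined in Section 5.2 for the planned paired tests?

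*Combined protocol and SAP*

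**What the plan says.** Section 3.1 sets the endpoint: "the four primary outcomes of T cell (CD4, CD8), NKT and NK cell numbers will be measured at pre-specified treatment time points". Section 8.1 fixes the comparison: "Using flow cytometry on peripheral blood obtained at baselines and after 3 cycles of therapy". Each of the four changes is tested with a two-sided paired t-test at 0.013, or a signed-rank test if the differences are not normal.

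Section 5.2 is the only place that says how the numbers are made, in three sentences.

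- Sorting: "PBMCs will be FACS-sorted into NK cells" and into CD4 and CD8 T-cell subsets, each with a marker phenotype. NKT is not among them.
- Measurement: the percentages of all four populations, NKT included, "will be determined by phenotypic analysis of peripheral blood mononuclear cells (PBMCs) stained for CD56, CD3, CD4, CD8, and CD16".
- Conversion to numbers per millilitre of blood: "the percentage of CD4 T or NK cells will be multiplied by the total lymphocyte count".

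On timing, Section 2.2.2 lists a CBC with differential under this rule: "The following studies and laboratory tests will be completed within 4 weeks prior to study entry". Section 2.4.1 has its own baseline window: "Research and clinical laboratory tests to be performed within 4 weeks of study entry and prior to starting therapy". Footnote i of the Study Calendar (Section 3.4) is narrower: "Blood for biomarker analysis will be collected on D1 (within 3 days prior) of Cycle 1, Cycle 2, Cycle 4, Cycle 7". Section 3.3.5.1 puts a CBC with differential on Day 1, within 3 days prior, of cycles 1, 2, 4 and 7. Section 5.3.3 refers the laboratory to Section 5.1 for methods, although they stand in Section 5.2.

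**The concern.** A primary variable should be reproducible from the plan. Read literally, Section 5.2 falls short in several ways.

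- NKT appears in neither the sorting list nor the conversion sentence, and the stained markers allow more than one gate. CD3+CD56+ is one. CD3+CD16+CD56+, by analogy with the stated NK phenotype, is another. Two analysts could build different NKT counts from the same tubes.
- CD8 has a phenotype but no written conversion.
- The percentage is taken on PBMCs while the multiplier is a lymphocyte count, so the two bases might not match.
- The lymphocyte count multiplies all four percentages. If the baseline value came from a screening CBC and the flow sample from another day, one mismatched number would enter all four paired differences.
- The CD4 and CD8 phenotypes do not exclude CD56, so a cell might be counted under two outcomes.

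At stake would be the meaning of the NKT result, the accuracy of all four baseline values, and a choice of gate made after the data had been seen.

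**Working it through.** **1. The plan's own figure.** Inputs from Section 8.1: n = 28, effect 0.67 SD of the paired difference, two-sided 0.013. The noncentrality is 0.67 × √28 = 3.55 on 27 degrees of freedom. The exact noncentral-t power is 80.4%, and the smallest n that reaches 80% is 28, so the stated 80% reproduces. At 0.05/4 = 0.0125 the power is 79.97%, which is the same figure for practical purposes. The effect is set in SD units of the difference, so no choice of gate, parent population or CBC alters n or the power at that effect size.

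**2. What is written for each outcome in Section 5.2.**

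| Outcome | Phenotype in sorting sentence | In measurement sentence and panel | Named in conversion |
|---|---|---|---|
| CD4 | yes | yes | yes |
| CD8 | yes | yes | no |
| NK | yes | yes | yes |
| NKT | no | yes | no |

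The sorting sentence is not the endpoint definition. Its sorted NK cells are the effectors in the lysis assay described later in Section 5.2. The endpoint rests on the measurement sentence, which covers all four populations. The conversion follows directly and has a general aim, numbers per millilitre, so naming CD4 and NK reads as shorthand. No other conversion is offered for CD8 or NKT, and Section 3.1 requires numbers for both.

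**3. Parent population.** Let p be the percentage, L the lymphocyte count and m the non-lymphocyte share of PBMCs. If p is a share of lymphocytes, p × L is cells per millilitre. If p is a share of PBMCs, p × L is (1 − m) times the true count. The documents give no value of m. On assumed values, m moving from 20% to 30% with no true change gives 0.70/0.80 − 1 = −12.5%, and the reverse gives 0.80/0.70 − 1 = +14.3%. Those errors arise only under a reading that fails to deliver what the section says it computes. The lymphocyte multiplier therefore points to a lymphocyte parent.

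**4. Which lymphocyte count.** The Study Calendar leaves biomarker blood blank in the pre-treatment column and marks it at Cycle 1 Day 1, where routine labs are also marked. Footnote i and Section 3.3.5.1 give both the same window, Day 1 or within 3 days prior, at cycle 1 and at cycle 4. Inside that window the draws are at most 3 days apart, or somewhat more if footnote k's ± 3 days is used. A 28-day gap needs a screening CBC taken 28 days before entry, a flow sample taken at entry against the calendar, and disregard of the scheduled Cycle 1 Day 1 CBC. Section 2.4.1 is an outer limit for all baseline tests, and the calendar's window lies inside it.

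**5. Choice of NKT gate.** With one gate g used at both times, the analysed difference is D(g) = count after cycle 3 under g minus baseline count under g. Its null hypothesis is a zero mean change in that population. The test is valid for any g fixed in advance; g decides only which cells the conclusion describes.

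**6. Overlap.** Section 8.1 tests each count separately. Nothing in the plan sums the four or requires them to be disjoint, so an overlap breaks no rule.

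**The case for a change.** The strongest reply is that multiplicity carries the NKT gap into the other tests. Section 8.1 allows Hochberg in place of Bonferroni. Suppose CD4, CD8 and NK each give p = 0.04. If NKT also gives 0.04, the largest p is below 0.05 and all four are rejected. If NKT gives 0.06, that step fails, 0.04 exceeds 0.05/2 = 0.025 and the stricter limits after it, and none is rejected. An analyst free to choose the NKT gate after seeing the data could decide all four results.

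The arithmetic stands. It describes selection after the fact, however, and no rule in the plan calls for that. Any of the four p-values has the same leverage under Hochberg. Under the stated Bonferroni levels, suppose someone tried two NKT gates and kept the better. The familywise bound would go from 4 × 0.013 = 0.052 to 5 × 0.013 = 0.065, so even that misuse has a small ceiling.

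It is also fair to say that other assays are specified more fully (the lysis assay has a formula and effector-to-target ratios), and that Section 9.2 foresees shipping samples to another institution, where written gates help. That supports good laboratory records. It does not show that any stated rule gives a wrong result.

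**Conclusion.** The textual gaps are real: no NKT gate is written, and the conversion names two of the four counts. They are missing detail that a flow laboratory and an analyst would fill in the obvious way: one lymphocyte-based conversion for all four counts, the Day 1 CBC with differential at cycles 1 and 4, and one NKT gate from the markers already stained, used at both time points. The Section 5.3.3 pointer to 5.1 is a clerical slip.

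No bias, loss of power or inflation of error is shown. Power stays at 80.4% for 28 patients. The 12.5% and 14.3% shifts rest on assumed non-lymphocyte shares and on the less sensible parent population, and the 28-day gap requires the calendar to be ignored.

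The conclusion rests on two assumptions: that the calendar's Day 1 window is followed at baseline, and that the NKT gate is settled without reference to the change results. Nothing in the documents suggests otherwise. Section 8.1 also says the results will be presented descriptively, so little turns on a single threshold. No change to the plan is needed.
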